9.6. Data management

HPHCI, located in Boston, Massachusetts, will serve as the Coordinating Center for the proposed study. HPHCI staff or contractors will be responsible for writing and distributing SAS programs that can be used to evaluate data from the administrative claims databases at participating DPs. The distributed network will allow DPs to maintain physical and operational control of their data while allowing use of the data to meet the study needs. HPHCI will maintain a secure distributed querying web-based portal to

214420 (EPI-ZOSTER-039 VS US DB) Protocol Amendment 2 Final

enable secure distribution of analytic queries, data transfer and document storage. The system will meet all required State and Federal security guidelines for health data (e.g., Federal Information Security Management Act (FISMA), Health Insurance Portability and Accountability Act of 1996), specifically FISMA compliant for FISMA security controls as specified in the National Institute of Standards and Technology (NIST) Special Publication 800-53 ([NIST, 2021] and Joint Task Force Transformation Initiative 2017).

HPHCI brings expertise in conducting multi-site evaluations using disparate electronic healthcare data systems, including extensive work with the Health Care Systems Research Network, the VSD, FDA Sentinel, the National Institutes of Health, Health Care Systems Research Collaboratory, the Innovation in Medical Evidence Development and Surveillance (IMEDS) program, the Biologics and Biosimilars Collective Intelligence Consortium (BBCIC) and Patient-Centered Clinical Research Network (PCORnet). HPHCI will oversee all project activities, including scientific leadership, management of the partnership, coordination of activities with the DPs and other participants, oversight of the project plan and budgets, establishment of secure infrastructure used for collaboration, and training related to use of the SCDM and associated querying tools. The DPs will establish and maintain the administrative, hardware, and software capabilities and capacity to respond to data requests in a timely manner. They will also provide data science support with epidemiologic review.

9.6.1. Data Collection Period

Data collection (start of study period) is anticipated to begin July 1, 2021. As the number of pregnant women with IC conditions who receive HZ/su during pregnancy is expected to be small, two steps are proposed for this study. A feasibility assessment (Section 9.6.1.1) will be conducted first to determine whether sufficient numbers of live births from vaccinated pregnant women with IC conditions could be identified, followed by either a cohort study or descriptive analysis depending on the outcome of the feasibility assessment (see Figure 1).

The feasibility assessment will identify live birth deliveries from vaccinated and unvaccinated pregnant women with IC conditions for two years (July 1, 2021, to June 30, 2023). When the feasibility assessment is completed, the total number of eligible (HZ/su-exposed with live birth) pregnancies will be calculated. If target numbers are reached a full-scale cohort study will be conducted. If target numbers are not reached in the feasibility assessment period, a descriptive analysis will be conducted (see Section 9.7.3).

The cohort study will identify HZ/su exposed and unexposed pregnancies for 5 years (July 1, 2021 to June 30, 2026), including 2 years rolled from the feasibility assessment and 3 additional years. The last pregnant woman will be enrolled on June 30, 2026; but, since the expected pregnancy period will be approximately 9 months, follow-up of pregnant women will continue until March 30, 2027. Infants will be followed for up to one year after birth, with data collection ending Q1 2028. Data tables will be completed in Q3 2028. The clinical study report will be completed on April 30, 2029 and submission of the clinical study report to FDA will be completed on December 30, 2029.

214420 (EPI-ZOSTER-039 VS US DB) Protocol Amendment 2 Final

The descriptive analysis will include HZ/su exposed and unexposed pregnancies (live birth and non-live birth pregnancies) among women with IC conditions identified in the feasibility assessment and their infants (July 1, 2021 to Jun 30, 2023). Infants will be followed up for up to one year after birth, with data collection ending in Q1 2025. The clinical study report will be completed in Q3 2026 and submission of the clinical study report to FDA will be completed in Q4 December 2026.

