9. RESEARCH METHODS

9.1. Study design

A population-based, non-interventional cohort study will be performed to identify and assess birth and pregnancy outcomes from HZ/su exposed pregnancies among women ages 18-49 years with IC conditions. A comparison group of pregnancies among women with IC conditions who were not exposed to HZ/su during pregnancy will be included and will serve as a reference to account for the contribution of different IC conditions on the safety outcomes of interest. The study will be conducted using health data held by three Data Partners that participate in the FDA's Sentinel System (described in Section 9.4).

The study period for identification of exposed and unexposed pregnancies for the cohort study will be July 1, 2021 to June 30, 2026. MCMs and additional infant outcomes (preterm birth, SGA, LBW, NICU admission, neonatal death) will be assessed in pregnancies resulting in a live birth for which the mother is linked to an infant. Since infant outcomes are generally captured in the infant's health plan claims, the mother's and infant's claims will be linked (see Section 9.2.1). Infants born from these pregnancies (exposed and unexposed) will be followed for up to one year of age for assessment of MCMs, the primary outcome of interest. Pregnancy outcomes will be assessed in pregnancies resulting in a live birth, non-live birth (stillbirth, spontaneous abortion).

214420 (EPI-ZOSTER-039 VS US DB) Protocol Amendment 2 Final

MCMs identified from this study will be validated by board certified teratologists. The teratologists will review the medical charts of each potential case and be blinded to treatment. Only validated cases will be used for main descriptive or comparative analyses (see Section 9.3.2).

Prior to initiating a cohort study, a feasibility assessment will be conducted (see Section 9.6.1.1) to identify counts of exposed live birth pregnancies during the period July 1, 2021 to June 30, 2023. If the feasibility assessment determines that it is not possible to identify an adequate number of exposed live birth pregnancies (see Section 9.5) among women with IC conditions for a cohort study (i.e., $\geq 1/3$ overall target), a descriptive analysis will be conducted (Section 9.7.3). The descriptive analysis will include HZ/su exposed and unexposed pregnancies (live birth and non-live birth pregnancies) among women with IC conditions identified in the feasibility assessment and their infants.

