9.2.1. Study Population (Amended 15 August 2022)

The study population will include pregnancies among women who are diagnosed with IC conditions, with pregnancy start dates occurring during the period July 1, 2021 to June 30, 2026 (see Section 9.2.1.1 for description of the algorithm for estimation of pregnancy start dates). Singleton pregnancies among women who are diagnosed with IC conditions of systemic lupus erythematosus (SLE), multiple sclerosis (MS), rheumatoid arthritis (RA), IBD, PsO or psoriatic arthritis (PsA), solid organ transplant (SOT), stem cell transplant (SCT), hematologic malignancies (HM), solid tumors (ST), and human immunodeficiency virus (HIV) prior to and during early pregnancy will be identified from the DRN. Validated algorithms in the CBER BEST assessment report [Saunders-Hastings, 2021 will be used to identify IC conditions including solid organ transplant (SOT), stem cell transplant (SCT), hematological malignancy (HM), solid tumor (ST,) human immunodeficiency virus (HIV), as these are specific to each IC condition as well as valid and consistent with the typical approaches that are used in Sentinel, as shown in Appendix B: Validated Coding Algorithms for IC conditions. ICD-10-CM Codes for IC (Appendix A) and validated coding algorithms that have high positive predictive values (PPVs), i.e. >75%, will be used to identify study participants who are IC. These IC conditions were selected because they have the highest risk of HZ, with a high prevalence in pregnant women with IC conditions (see Table 1).

For autoimmune diseases (AIDs) (systemic lupus erythematosus [SLE], multiple sclerosis [MS], rheumatoid arthritis [RA], inflammatory bowel disease [IBD], psoriasis [PsO], and psoriatic arthritis [PsA]), coding algorithms from the literature that are AID-specific (Appendix B) will be used instead of the coding algorithms in the CBER BEST assessment report [Saunders-Hastings, 2021], as the algorithms that are presented in this report are not AID-specific.

Pregnancies will be included in the study if the following inclusion criteria are met:

- Participant who is pregnant with a pregnancy start date between July 1, 2021 and June 30, 2026. Live births are to be followed for 1 year.
- Participant is a female aged 18-49 years on the pregnancy start date.

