9.2.1.1. Identification of Pregnancy Episodes and Gestational Age Assumptions

Sentinel investigators have developed publicly available tools to define medication exposures during pregnancy and comparatively assess pregnancy outcomes. These tools use a claims-based algorithm previously validated in the FDA-sponsored Medication Exposure in Pregnancy Risk Evaluation Program (MEPREP). The current study will use this algorithm to identify pregnancies ending in live births through identification of diagnosis and procedures codes listed in Appendix E: Live Birth Diagnosis and Procedure Codes. Because the date of the last menstrual period (LMP) is not available in the health plan data, the algorithm calculates the length of the pregnancy episode and the start of the pregnancy (i.e., LMP) using International Classification of Diseases, Tenth Revision, Clinical Modification (ICD-10-CM) codes indicative of weeks of gestation, as well as ICD-10-CM codes for preterm and post-term deliveries in the inpatient care setting (Appendix F: Codes to Identify Preterm and Post-term Birth). Specifically, the algorithm first prioritizes codes specifying completed weeks gestation, then non-specific preterm delivery codes (codes that indicate preterm birth but do not indicate a specific gestational age), and lastly non-specific post-term delivery codes (codes that indicate post-term birth but do not indicate a specific gestational age) identified within 7 days of

214420 (EPI-ZOSTER-039 VS US DB) Protocol Amendment 2 Final

the delivery encounter. ICD-10-CM incorporates diagnosis codes for gestational age in weekly increments. We assume the approximate mid-point of the specified gestational age (e.g., assumption of 263 days [37 weeks and 4 days] for ICD-10-CM code Z3A.37 [37 completed weeks gestation]). Gestational age assumptions are listed in Appendix F: Codes to Identify Preterm and Post-term Birth. If gestational age, preterm birth, or post-term delivery codes are not identified within 7 days of the delivery encounter, then the default assumption for gestational age for live birth deliveries is 273 days, based upon gestational lengths reported in published studies [Davidoff, 2006; Margulis, 2013]. The pregnancy start date (i.e., LMP) is then calculated by subtracting the gestational age from the date of the live birth delivery.

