9.6.1.1. Feasibility Assessment

During the feasibility period, annual assessments will be conducted to summarize the counts of HZ/su-exposed and unexposed live birth pregnancies among women with IC conditions (18-49 YOA). The counts of exposure to at least one dose of HZ/su will be stratified by calendar year of delivery, maternal age at pregnancy start date (5-year age groups), and IC condition.

Counts of women of childbearing age (18-49 YOA) with IC conditions who are HZ/su-exposed and unexposed will similarly be determined.

If the number of HZ/su-exposed pregnancies (live birth pregnancies linked to an infant) identified during the feasibility assessment is equal to or above 1/3 of the number of HZ/su-exposed pregnancies needed for the cohort study (n = 711 for cohort study and n = 237 for feasibility assessment, respectively), the feasibility assessment outcome will be categorized as 'Yes'. This indicates the target number of exposed pregnancies linked with live births could probably be identified during the five-year cohort study identification period, although it is not guaranteed.

If the number of HZ/su pregnancies identified during the feasibility assessment is less than one third of the target number of exposed pregnancies needed for the cohort study (i.e., n > 237), the feasibility assessment outcome will be categorized as 'No'. Should this be the case, the descriptive analysis, rather than the cohort study, will be conducted.

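### Section 9.6.1 words the feasibility count by delivery date while the cohort and the protocol's calendar run on pregnancy start date; read literally, about 15 of 24 months could count toward 237

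*Protocol*

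**What the plan says.** **Feasibility window.** Section 9.6.1 has the assessment identify "live birth deliveries from vaccinated and unvaccinated pregnant women with IC conditions for two years (July 1, 2021, to June 30, 2023". Section 9.1 gives the same dates but only says that the aim is "to identify counts of exposed live birth pregnancies during the period July 1, 2021 to June 30, 2023", without stating whether start or delivery must fall in the period. The abstract is equally silent. Section 9.6.1.1 stratifies the exposed counts by calendar year of delivery.

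**Cohort.** Section 9.2.1 admits a "Participant who is pregnant with a pregnancy start date between July 1, 2021 and June 30, 2026". Section 9.6.1 describes the five cohort years as "including 2 years rolled from the feasibility assessment and 3 additional years".

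**Decision rule.** Section 9.6.1.1 sets the threshold at one third of the exposed target ("n = 711 for cohort study and n = 237 for feasibility assessment, respectively"), counted in live birth pregnancies linked to an infant. Below it, "the descriptive analysis, rather than the cohort study, will be conducted".

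**Calendar.** Section 9.6.1.2 places identification of the feasibility live-birth pregnancies in 2021-2024. For the descriptive analysis, section 9.6.1 states: "Infants will be followed up for up to one year after birth, with data collection ending in Q1 2025".

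**The concern.** Two years of deliveries are not the first two years of pregnancy starts; the windows are about nine months apart. If the delivery wording governs and only pregnancies that can enter the cohort are counted, the first nine months of the window hold almost no countable births. Pregnancies that start in its last nine months are mostly undelivered when it closes. The 237 threshold makes no allowance for this.

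The count is the only stated switch between the two analyses. A No replaces the comparison that is the primary objective with prevalences and confidence intervals and no statistical comparison. A go/no-go rule should not have two readings that can give opposite answers on the same data.

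**Working it through.** **Inputs from the protocol**
- Delivery window: July 1, 2021 to June 30, 2023 (9.6.1).
- Cohort pregnancy starts: July 1, 2021 to June 30, 2026 (9.2.1), which is 1,826 days or 60 months.
- Gestation: "the default assumption for gestational age for live birth deliveries is 273 days" (9.2.1.1).
- Threshold 237 and exposed target 711 (9.6.1.1).

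**Assumption not in the protocol:** exposed linked live births accrue at a constant rate by start date. The protocol gives no accrual curve.

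**1. The plan's own figure.** 711 / 3 = 237, as stated.

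**2. Which reading fits the calendar?**
- Start-date window: June 30, 2023 + 273 days = March 29, 2024; one more year gives March 29, 2025, which is Q1 2025 as stated.
- Delivery window: June 30, 2023 + 1 year is the end of June 2024, which is Q2 2024 and does not match.
- The cohort calendar follows the start-date logic: June 30, 2026 + 273 days = March 30, 2027, and one more year ends in Q1 2028. Both match 9.6.1.

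**3. What the literal delivery window covers, for cohort-eligible pregnancies**
- First delivery at default gestation: July 1, 2021 + 273 days = March 31, 2022.
- Last start that delivers in the window: June 30, 2023 − 273 days = September 30, 2022.
- Starts covered: July 1, 2021 to September 30, 2022 = 457 days, about 15.0 months.
- Share of the two years: 457 / 730 = 62.6%.
- For gestations of 284 to 256 days the cover is 14.7 to 15.6 months.

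**4. Expected counts at a constant pace giving exactly 711 in five years**

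| Window | Calculation | Expected count | Against 237 |
|---|---|---|---|
| Start date, 730 days | 711 × 730 / 1,826 | 284 | Yes |
| Delivery date, 457 days | 711 × 457 / 1,826 | 178 | No |

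Over the gestation range above, the delivery-date count is 174 to 185. If counts are Poisson, the chance of reaching 237 is about 99.8% on the start-date reading and about 0.001% on the delivery reading.

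**5. Five-year pace needed to reach 237**
- Start date: 237 × 1,826 / 730 = about 593.
- Delivery date: 237 × 1,826 / 457 = about 947.

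Constant paces from 711 to just under about 947 would meet the cohort target yet return No on the delivery reading.

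**6. Sensitivity to rising uptake.** Let the rate rise linearly from 0.5 to 1.5 times the mean of 711 / 60 = 11.85 per month. The cumulative count at month t is 11.85 × (0.5t + t²/120).
- t = 24: 11.85 × 16.8 = 199.
- t = 15.0: 11.85 × 9.39 = 111.

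Both fall below 237. The ratio of the two counts worsens (111/199 = 56%, against 63% at constant pace), but the absolute gap narrows from 106 to 88.

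**The case against.** The strongest reply is that the delivery reading rests mainly on one word in one sentence, and most of the document points the other way. The abstract and 9.1 speak of live birth pregnancies. Section 9.6.1.2 runs identification into 2024. The Q1 2025 end of follow-up fits only a start-date window. Stratifying by year of delivery is a choice of table layout. Analysts following their own calendar would use start dates, and a study on constant pace would then pass with 284. Figure 1, which sets out these timelines, is not visible in the text available to us. All of this stands, and it makes the point an internal contradiction rather than a settled rule that fails the study.

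Two further limits also stand. First, the 15 months needs the delivery window and the start-date criterion applied together. Section 9.6.1 says that eligible pregnancies are totalled, which supports this, but no section states the combination for the 237 count. If all deliveries counted, births from pregnancies begun before July 2021 would enter; those pregnancies cannot join the cohort, so that reading is no better. Second, the threshold is one third, below the pro-rata two fifths (237 against 284). That margin helps but does not cover a 15-month window.

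What does not stand is the suggestion that nothing needs changing. The sentence in 9.6.1 is explicit, and no section says which date anchors the count.

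**Conclusion.** The concern holds as an inconsistency in the wording of a decisive rule. The delivery wording in 9.6.1 conflicts with the start-date definition of the cohort, with the rolling of the two years into it, and with the protocol's timelines. Taken literally with cohort eligibility, it cuts the countable starts to 457 of 730 days. It could also turn a Yes (about 284) into a No (about 178) for a study on constant pace for 711.

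A reader might infer that the protocol fixes a delivery cut-off and that any study fast enough to reach 711 would be cancelled. The documents do not support that. Their calendar favours start dates; the wrong answer arises only at constant paces from 711 to just under about 947; and a No leads to a descriptive analysis in matched cohorts, not to cancellation. Nor does correcting the wording guarantee a Yes: in the rising-uptake example both readings fail. The counts of 178 and 284 illustrate constant accrual with 273-day gestation and are not forecasts.

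**What to change.** In section 9.6.1, and in the same terms in the abstract, 9.1 and 9.6.1.1, state that the count compared with 237 covers HZ/su-exposed live birth pregnancies linked to an infant whose pregnancy *start* date lies from July 1, 2021 to June 30, 2023. State also that the decision is taken only after their births have been observed, to about the end of March or April 2024.

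If a delivery cut-off is really intended, say so, say whether the start-date criterion also applies, and rescale the threshold to the roughly 15 months of starts that it covers. Keeping the same required pace would give 237 × 457 / 730 = about 148.

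The cost of the preferred change is protocol wording. The decision date fits the 2021-2024 surveillance period and the Q1 2025 end of infant follow-up, so no other milestone has to move.

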9.6.1.1. Feasibility Assessment

During the feasibility period, annual assessments will be conducted to summarize the counts of HZ/su-exposed and unexposed live birth pregnancies among women with IC conditions (18-49 YOA). The counts of exposure to at least one dose of HZ/su will be stratified by calendar year of delivery, maternal age at pregnancy start date (5-year age groups), and IC condition.

Counts of women of childbearing age (18-49 YOA) with IC conditions who are HZ/su-exposed and unexposed will similarly be determined.

If the number of HZ/su-exposed pregnancies (live birth pregnancies linked to an infant) identified during the feasibility assessment is equal to or above 1/3 of the number of HZ/su-exposed pregnancies needed for the cohort study (n = 711 for cohort study and n = 237 for feasibility assessment, respectively), the feasibility assessment outcome will be categorized as 'Yes'. This indicates the target number of exposed pregnancies linked with live births could probably be identified during the five-year cohort study identification period, although it is not guaranteed.

If the number of HZ/su pregnancies identified during the feasibility assessment is less than one third of the target number of exposed pregnancies needed for the cohort study (i.e., n > 237), the feasibility assessment outcome will be categorized as 'No'. Should this be the case, the descriptive analysis, rather than the cohort study, will be conducted.

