9.5. Study size

All pregnancies among women who meet the study inclusion/exclusion criteria will be included in this study.

As the IC conditions included are heterogeneous and the number of MCMs for the primary outcome is likely small, the prevalence of each MCMs among each IC condition under study is not available. For sample size calculation for the cohort study, we employed the prevalence of overall MCMs (3%) in the general population [Holmes, 1976; Leppig, 1987; Marden, 1964; Van Regemorter, 1984] which might have a lower prevalence than among women with IC conditions. Therefore, the sample size calculated is relatively conservative. Assuming a 1:3 ratio of HZ/su-exposed to unexposed, a type 1 error of 0.05, and a target risk ratio of 2.0 for the primary safety outcome of MCMs, 711 live birth infants (live birth pregnancies linked to infant records) from the HZ/su-exposed group and 2133 live birth infants from the unexposed group will allow us to achieve 90% power.

The Power Analysis and Sample Size software (NCCS Statistical Software) was used in the sample size calculation.

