9.7.2. Cohort Study

If the feasibility assessment (Section 9.6.1.1) identifies that the number of HZ/su-exposed pregnancies is equal to or above the target number of exposed pregnancies, a subsequent cohort study will be conducted.

Infant/birth outcomes and pregnancy complications will be assessed among eligible live birth pregnancies linked to infant records. Pregnancy outcomes will be assessed in the population of all pregnant women meeting eligibility criteria.

Propensity scores and matching will occur within each Data Partner. Potential confounders are described in Section 9.3.3. The methodology will be described in detail in the Statistical Analysis Plan (SAP).

9.7.2.1. Primary Objective and Secondary Objective 1

The Mantel-Haenszel Chi-square test or Fisher exact test (univariate analysis), wherever appropriate, will be employed to compare the prevalence of the primary outcome (MCMs) between eligible live birth pregnancies among women with IC conditions who were vaccinated with HZ/su during pregnancy and those who were not vaccinated with HZ/su during pregnancy. Multivariable conditional logistic regression will be conducted to adjust for potential residual confounding after matching if there is statistical significance in univariate analysis. In addition, the prevalence of MCMs and their associated 95% CIs will be calculated among women with IC conditions who were exposed to HZ/su during pregnancy versus the corresponding matched women who were not exposed to HZ/su during pregnancy. All analyses will be stratified by stage of pregnancy (pre-pregnancy, first trimester, second trimester, third trimester).

Similar methods will be used for each of the secondary infant/birth outcomes (e.g., preterm birth, SGA, LBW, NICU admission, neonatal death).

9.7.2.2. Secondary Objective 2

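### The feasibility go/no-go rule is misprinted: Section 9.6.1.1 reverses the inequality for 'No', and Sections 9.6.1 and 9.7.2 omit the one-third fraction

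*Protocol*

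**What the plan says.** The cohort study needs "711 live birth infants (live birth pregnancies linked to infant records) from the HZ/su-exposed group" (Section 9.5). Section 9.6.1.1 derives the feasibility threshold from this: "n = 711 for cohort study and n = 237 for feasibility assessment, respectively".

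The decision rule then appears in five places:

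- **Section 9.6.1.1, *Yes*:** the count of linked exposed live birth pregnancies "is equal to or above 1/3 of the number of HZ/su-exposed pregnancies needed for the cohort study".
- **Section 9.6.1.1, *No*:** the count is "less than one third of the target number of exposed pregnancies needed for the cohort study (i.e., n > 237".
- **Section 9.7.2:** if the feasibility assessment, cited as Section 9.6.1.1, finds that "the number of HZ/su-exposed pregnancies is equal to or above the target number of exposed pregnancies, a subsequent cohort study will be conducted".
- **Section 9.6.1:** the full cohort study follows if target numbers are reached. "If target numbers are not reached in the feasibility assessment period, a descriptive analysis will be conducted".
- **Sections 9.1 and 9.7.3:** both use the one-third rule. Section 9.1 treats at least one third of the overall target as adequate, and Section 9.7.3 sends a count below one third to the descriptive analysis.

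The counting base is also worded in different ways. The *Yes* rule requires linkage to an infant. The *No* rule and Section 9.6.1 do not mention linkage. Section 9.6.1 says "The feasibility assessment will identify live birth deliveries from vaccinated and unvaccinated pregnant women with IC conditions for two years", whereas Section 9.2.1 defines eligibility by pregnancy start date.

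**The concern.** The feasibility outcome settles whether the study makes any comparison at all. On *No*, the protocol allows only prevalences with confidence intervals and no statistical comparison (Abstract, Sections 8 and 9.7.3). A rule with that consequence should give one answer for each possible count and the same answer wherever it is stated.

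As printed, it does neither. The only numeric statement of the *No* condition has the wrong sign, and two sections that restate the rule leave out the fraction that makes 237 the threshold. If the count falls between 237 and 710, someone could point to one section to justify running the cohort study and to another to justify not running it, after the count is known.

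**Working it through.** **Threshold.** 711 / 3 = 237 exactly, so the protocol's own figure reproduces. The 711 is taken here as stated in Section 9.5. If it were revised, 237 would move with it.

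**Meaning of target number in Section 9.6.1.1.** The *No* rule speaks of one third of the target number and puts that third at 237. The target number in that sentence is therefore 3 × 237 = 711. The section never calls 237 the target number.

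**Each rule applied to each range of counts n:**

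| n | 9.6.1.1 *Yes* rule | 9.6.1.1 *No* rule, words | 9.6.1.1 *No* rule, symbol | 9.7.2 if target = 711 | 9.7.2 if target = 237 | 9.7.3 |
|---|---|---|---|---|---|---|
| 0–236 | not met | *No* | not met | not started | not started | descriptive |
| 237 | *Yes* | not met | not met | not started | started | not descriptive |
| 238–710 | *Yes* | not met | *No* | not started | started | not descriptive |
| 711 or more | *Yes* | not met | *No* | started | started | not descriptive |

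- *Within 9.6.1.1:* the *Yes* rule and the printed symbol are both met for every n of 238 or more. For 0 to 236 the words say *No* and the symbol does not.
- *Across sections:* with the target read as 711, counts of 237 to 710 are *Yes* in 9.6.1.1, are not started by 9.7.2, and are not sent to the descriptive analysis by 9.7.3. Section 9.6.1, read the same way, would send them to the descriptive analysis.
- *Example, n = 300:* *Yes* by the first rule, *No* by the symbol, no start under 9.7.2 at 711, and no descriptive analysis under 9.7.3.

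**After correction** (*No* if n < 237, *Yes* if n ≥ 237, the same threshold in 9.6.1 and 9.7.2), the two outcomes cover every count once and agree with 9.1 and 9.7.3.

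**Counting base.** Section 9.6.1 ends descriptive data collection in Q1 2025. From 30 June 2023, about 9 months of gestation plus 1 year of infant follow-up reaches the end of March 2025. The cohort timeline has the same form: 30 June 2026, then 30 March 2027, then Q1 2028. Both fit a window defined by pregnancy start dates.

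**Supporting note on accrual.** Section 9.6.1.1 says of a *Yes*: "This indicates the target number of exposed pregnancies linked with live births could probably be identified during the five-year cohort study identification period", and adds that this is not guaranteed. At a constant rate, 237 in 24 months gives 237 × 60/24 = 592.5, about 593 in five years, and 592.5/711 = 83%. Reaching 711 needs (711 − 237)/36 = 13.2 per month, against 237/24 = 9.9 per month so far. That is a rise of about one third.

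**The case against.** The strongest reply is that nobody would be misled. The sentence with the wrong sign says in words that the count is below one third. The *Yes* rule just before it, Section 9.1 and Section 9.7.3 all say the same. Four statements agree against one symbol, so it is very probably a slip. This stands as to intent. It does not remove the need to correct the only number attached to the *No* rule.

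A reader might infer that Section 9.7.2 demands all 711 within two years, so that the protocol orders opposite decisions for 237 to 710. The documents do not establish that. Section 9.7.2 cites 9.6.1.1, which gives 237 as the feasibility number. It says that the cohort study follows if the target is reached, not only if. Needing 711 in two years would also make the three further years of identification unnecessary for sample size. What remains is loose wording that has a conflicting literal reading.

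A reader might also infer that the feasibility count is of deliveries, or of unlinked live births, and so is not comparable with 711. The timeline in 9.6.1 fits start dates, and the operative *Yes* rule states linkage explicitly. The wording is uneven, but those readings are not supported.

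Finally, a reader might infer that 237 is too low a threshold because it projects to about 593. That assumes flat accrual, which the protocol does not claim. The window opens in the month the indication was expanded, Section 7 says exposures may increase, and 9.6.1.1 hedges its own statement.

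**Conclusion.** The point holds as a drafting error in an operative decision rule. The sign in Section 9.6.1.1 is reversed, which is certain from the text. The missing one-third fraction in 9.6.1 and 9.7.2 is an ambiguity: on the literal reading of target number as 711 it affects counts of 237 to 710, and on the likely reading as 237 it affects none. The size of the second part therefore depends on which reading is taken.

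The threshold of 237 is not shown to be wrong. The accrual projection shows only that the expectation of reaching 711 relies on the rate rising by about one third after the first two years.

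The error is more than clerical because this rule governs whether any comparative safety analysis is done. It should be corrected before the feasibility count is acted on.

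**What to change.** 1. In Section 9.6.1.1, print the *No* condition as n < 237.
2. In Sections 9.6.1 and 9.7.2, replace target number(s) with one third of the target (237 HZ/su-exposed live birth pregnancies linked to an infant), to match 9.1 and 9.7.3.
3. State the same count in each place: linked live births from eligible pregnancies with start dates from 1 July 2021 to 30 June 2023. In 9.6.1, reword the reference to deliveries accordingly.
4. Optionally, add to 9.6.1.1 that reaching 711 from 237 assumes accrual in the last three years about one third faster than in the first two.

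The cost is wording in three sections. No new data, no new analysis and no change to the threshold are needed.
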